BOKS in Revere Detailed Protocol**Study PI: [name], MPH****BOKS in Revere****Detailed Protocol**

Version Date 8/9/2018

Study PI: [name]

Chief, Division of General Academic Pediatrics, Department of Pediatrics
Massachusetts General Hospital for Children

Co-Investigators and Study Staff

- [name] (Co-I)
Research Fellow in the Division of General Academic Pediatrics, Massachusetts General Hospital for Children and Fellow in Pediatric Endocrinology, Massachusetts General Hospital for Children
- [name]
Project Manager, Massachusetts General Hospital for Children
- Research Assistants:
[name], [name], [name], [name], [name], [name], [name], [name], [name], [name], [name], [name], [name], [name], [name]

I. Specific Aims:

School-based physical activity interventions are an area of interest in the field of childhood obesity prevention. Preliminary evidence suggests that these efforts may have a positive impact on child health, however there is large heterogeneity in interventions. This study evaluates the outcomes of a widely available school-based physical activity program, with the primary research question addressing the efficacy of a before school program – as delivered in partnership with schools – in improving indicators of child wellbeing as well as measuring implementation and feasibility.

Phase I

The primary specific aim is to perform a qualitative evaluation of child participation in a before school physical activity intervention through:

- a. Interviews with parents to obtain a detailed view of what barriers parents endorse to physical activity and the role of school-based programming in overcoming these barriers

BOKS in Revere Detailed Protocol

Study PI: [name], MPH

- b. Standardized structured physical activity observation of physical activity

Phase II

The primary specific aims are to examine the extent to which the physical activity intervention, compared to the control condition, results in:

- c. Change in BMI and BMI z-score over a 12-week period.
- d. Change in cognitive function and child-reported quality of life.

The secondary aims are:

- a. To evaluate the impact of program participation on school-collected outcomes, including grades, attendance, and disciplinary reports.
- b. To objectively measure student levels of moderate-vigorous physical activity in intervention sessions.

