Students are eligible for participation in BOKS if they are (a) enrolled in the school in grades K-8 with (b) signed BOKS parental release form. In the school that independently held BOKS in Fall 2017, preference will be given to students who have not yet participated. Beachmont Elementary will limit participation to 1st through 5th grades as kindergarten students follow a different schedule.

Spring 2018 Session

For Beachmont Elementary and Garfield Middle School:

All students will receive the BOKS Registration packet approximately 3-4 weeks before their schools' planned start date that will include the following below. Recruitment information will explain that we are interested in better understanding the effects of physical activity programming on child physical health, quality of life, and school performance.

BOKS in Revere Detailed Protocol

Study PI: [name], MPH

- (1) Letter introducing the BOKS program and the research study
- (2) Fact sheet answering key questions regarding the program and study
- (3) BOKS Registration form

Children will be instructed to return the BOKS Registration Form if they would like to participate in the BOKS program. Once the BOKS Registration Form is received, children will then receive Research Consent Form in school to take home for their parents to review, to be completed if they would additionally like to participate in the BOKS study. All forms should be submitted approximately 1-2 weeks before the start of the Spring 2018 program.

In order to ensure equal access to the program, participation in the BOKS program will be by lottery and not first-come, first serve. This decision was made in conjunction with school principals to not give preference to students who turned in forms first. All children with completed BOKS registration forms-will be entered in the lottery. The lottery is held in partnership with schools and independent of the research process, and will be held following return of BOKS registration forms. Children may participate in BOKS without participating in the research study. If registration does not exceed 50 students for the Spring 2018 session, there will be no waitlist control group or need for randomization.

See schema for detailed timeline.

For Paul Revere Innovation School:

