Prior to planned intervention start, volunteers from each school (teachers, parents, or school nurses) will receive formal training regarding the BOKS curriculum in. This training will be conducted by the BOKS program per their standard procedure and will occur at one of the participating schools. Volunteers will be recruited from interested individuals within each school (identified by the principals; may include teachers, school nurses, or parents).

The intervention sessions will occur before school, 3 days/week, lasting 30-60 minutes, for 12-15 weeks (with schedule and start date to be determined by school principal, in accordance with school resources and needs). Two trained volunteers will be present for each physical activity session, with approximately 40-50 students total per session. In accordance with BOKS regulations, trainers must be CPR certified and parents will have signed a release for program participation (in addition to study consent). All physical activity sessions will occur within school gymnasiums. Trainers will not participate in data collection.

At the beginning of the BOKS program (within one week of the study start at schools with 12 week program or within 3 weeks of study start in schools with 15 week program), each intervention group and control group student will have height and weight measured by trained research staff at the school in a setting that ensures student privacy. Students will also complete a validated measure of pediatric quality of life as well as one iPad-based cognitive tasks (anticipated total time 30 minutes). Trained research staff will be present to guide students through the assessment (see Appendix 3). Evaluations will occur at the time of a non-academic school period or within BOKS programming. Intervention and control group children will not stay after-hours for completion of measures. These measures will be repeated at 12-week follow-up (+/-1 week). Although one school plans to continue for 15-weeks due to their academic calendar, follow-up measurements will occur at approximately 12-weeks intervals in all schools. Schools will provide student report cards/progress reports, attendance, and disciplinary reports, only for students with signed parental consent for the research study. These measures will be completed in both groups in both the Spring 2018 and Fall 2018

BOKS in Revere Detailed Protocol

Study PI: [name], MPH

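### The baseline window lets sessions fall before the reference value for change, the follow-up anchor is not stated, and the setting for the cognitive and quality-of-life tests is not fixed

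*Combined protocol and SAP*

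**What the plan says.** Section IV, Phase II, places the first measurement as follows: "At the beginning of the BOKS program (within one week of the study start at schools with 12 week program". The window is wider where the schedule is longer: "within 3 weeks of study start in schools with 15 week program". Sessions run three days a week for 12 to 15 weeks. On setting, the same section says "Evaluations will occur at the time of a non-academic school period or within BOKS programming" and "Intervention and control group children will not stay after-hours for completion of measures". On follow-up, it says "These measures will be repeated at 12-week follow-up (+/-1 week" in either direction), and that although one school runs for 15 weeks, "follow-up measurements will occur at approximately 12-weeks intervals in all schools".

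The Phase II aim in Section I is "Change in BMI and BMI z-score over a 12-week period". Section VI bases the primary analyses on change from baseline. It adjusts for age, sex, school and SES, and lists program attendance among the possible effect modifiers. Section III (Consent, Fall 2018) keeps children who consented in Spring in the Fall measurements whether or not they attend BOKS in the Fall.

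For timing, Section III (Spring 2018 Session) adds "See schema for detailed timeline". That schema is Appendix 11. Neither it nor Appendix 3 (child measures) is in the text available for this review.

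**The concern.** A change score is only as clean as its starting value. If a child has already attended sessions when baseline is taken, any early program effect is in the reference value and drops out of the measured change. A school term or a control group does not put it back. How much drops out can vary by child and by school, because the two windows differ. Baseline carries extra weight here, since Spring 2018 had no wait-list control group and Fall 2018 is not randomized (Section III).

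Test setting is a separate matter. A Flanker test or PedsQL questionnaire done in a quiet school period at one visit and within BOKS programming at the other may differ for reasons unrelated to the program. Children measured without attending BOKS would ordinarily not be at BOKS programming, so setting could also track group. Section VI has no covariate for it.

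**Working it through.** The plan gives no figure of its own on this point, so there is none to reproduce. The check is arithmetic on the schedule.

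**Inputs (Section IV, Phase II).** Three sessions a week; program length L = 12 or 15 weeks; baseline within 1 or 3 weeks of study start; follow-up at 12 weeks, give or take 1.

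**Assumptions.** Study start is program start, and no sessions are cancelled. Both sides of the start are computed, because *within* may include days before it.

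**Step 1: sessions that can precede baseline (maxima within the stated windows).**
- 12-week schools: 3 × 1 = 3 of 3 × 12 = 36.
- 15-week school: 3 × 3 = 9 of 3 × 15 = 45.

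Section IV also allows individual outreach to absent children and states no outer time limit. Baselines taken that way are not counted here.

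**Step 2: sessions between the two measurements.** With baseline in week b and follow-up in week f, the count is 3 × (min(L, f) − max(0, b)). Follow-up is f = b + 12 if counted from baseline and f = 12 if counted from program start.

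| Program | Baseline week | Counted from baseline | Counted from program start |
|---|---|---|---|
| 12 weeks | −1 | 3 × (11 − 0) = 33 | 3 × (12 − 0) = 36 |
| 12 weeks | 0 | 3 × (12 − 0) = 36 | 3 × (12 − 0) = 36 |
| 12 weeks | +1 | 3 × (12 − 1) = 33 | 3 × (12 − 1) = 33 |
| 15 weeks | −3 | 3 × (9 − 0) = 27 | 3 × (12 − 0) = 36 |
| 15 weeks | 0 | 3 × (12 − 0) = 36 | 3 × (12 − 0) = 36 |
| 15 weeks | +3 | 3 × (15 − 3) = 36 | 3 × (12 − 3) = 27 |

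Allowing the 1-week tolerance on follow-up, the full ranges are 30 to 36 (12-week schools) and 24 to 39 (15-week school).

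**Step 3: what a week-0 baseline would change.**
- 15-week school, from week +3: 36 − 36 = 0 sessions added if follow-up is counted from baseline; 36 − 27 = 9 if counted from program start.
- 15-week school, from week −3: 36 − 27 = 9 if counted from baseline; 0 if counted from program start.
- 12-week schools: at most 36 − 33 = 3.

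The follow-up anchor therefore matters as much as the baseline window.

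**Step 4: attendance modifier.** Section VI does not say which sessions count. In the 15-week school, with follow-up exactly 12 weeks after a week-0 or week-3 baseline, a full-program count includes 45 − 36 = 9 sessions outside the measured interval: the last 9 for week 0, the first 9 for week 3. In 12-week schools it includes 0 to 3.

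**Setting.** There is nothing to compute. Section IV permits two settings and, in the protocol text, no rule assigns them by visit or group or separates testing from exercise.

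**The case against.** The strongest reply is that the text permits an exposed baseline but does not show one. Study start is undefined, *within* may mean before, and Appendices 3 and 11 may settle both timing and setting. This stands, and it limits the point to what the protocol text allows. Against it, testing within BOKS programming at a baseline visit is ordinarily possible only once sessions have begun, so the forward reading is natural.

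A second reply is that the 3-week window looks designed to keep a 12-week interval inside a 15-week program. That is also fair. A reader might infer from 9 of 45 that a fifth of the effect, or of the exposure, is lost. The documents do not support this: they give no time course for the effect, and with follow-up counted from baseline a week-3 start still spans 36 sessions. The problem is then an exposed reference value, not a shorter interval.

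Third, a baseline before the first session does not make every child unexposed. Spring participants remain in Fall measurement, earlier participants are given lower preference but not excluded, and one school ran BOKS in Fall 2017. Such children may already have had a whole program. This stands.

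Fourth, the attendance modifier is simply undefined and may be meant to cover only the measured interval. The direction of any setting effect also cannot be derived from the documents. Both are correct.

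**Conclusion.** The point holds as a modest design weakness that is cheap to repair. Followed as written, the plan permits up to 3 of 36 or 9 of 45 sessions before the reference value for the primary change, and the analysis takes no account of them. In the 15-week school a week-3 baseline gives 36 or 27 sessions between measurements, depending on an anchor the plan does not state. The setting for Flanker and PedsQL is not held constant across visits or groups.

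These figures assume that study start is program start and that no sessions are cancelled. They are maxima of exposure, not estimates of bias. A reader might conclude that the results are biased by a known amount; neither the occurrence nor the size can be stated. The protocol is dated after Spring enrollment, so timing can be changed only for Fall 2018, and the documents do not say whether a 15-week schedule recurs then.

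**What to change.** For Fall 2018, first checking Appendices 3 and 11 for rules already in place:

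1. Define study start as the school's first BOKS session of the term, and state that the 12-week follow-up is counted from baseline.
2. Take baseline before the child's first session of the term where feasible, and close to it, since an early baseline shortens the program time covered. Measure children who are not attending BOKS in the same calendar window.
3. Give Flanker and PedsQL in the same type of setting at both visits and in all groups, not during or directly after exercise, and record the setting. Test late registrants in that same setting before their first activity.
4. For all children, Spring included, count sessions attended before baseline from the attendance log and flag participation in an earlier BOKS term. Limit the attendance modifier to sessions between the two measurements. Report the primary change with and without children exposed before baseline, or by number of sessions before baseline if exclusion would remove a school.

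**Cost.** Measurement days become tighter, because children may not stay after hours. For 40 to 50 program children at about 30 minutes each, the load is 40 × 0.5 = 20 to 50 × 0.5 = 25 child-hours per school, less where children under 8 have only height and weight. Non-attending Spring participants add to this: with 100 children in total (an assumption), it is 100 × 0.5 = 50. Fall consent closes when baseline starts, so the cut-off moves earlier by up to 1 week, or up to 3 in a 15-week school, and some late registrants may be lost. In a 15-week school with a week-0 baseline, the last 3 × (15 − 12) = 9 sessions fall after follow-up (6 to 12 with the 1-week tolerance). Item 4 uses attendance already taken at each session.

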primary analyses will be based on change from baseline to follow-up with each outcome variable, with comparison performed between intervention and control group at each time. For all continuous variables, we will use t-tests for initial comparison between groups, followed by linear regression to control for potentially confounding variables (age, sex, school, SES) or potential effect modification (program attendance/MVPA level, parental PA support, baseline PA level, baseline BMI). For all binary variables, we will use Chi Square tests to evaluate for differences between groups at baseline and follow-up, followed by logistic regression to evaluate for confounding or effect modification. All analyses will be done in SAS under the guidance of a statistician.

Transcriptions from qualitative interviews will be reviewed by two study staff members to identify themes. Results from structured physical activity observation will provide descriptive statistics regarding individual program content and will be used as a measure of program implementation along with accelerometer data.

VII. Monitoring and Quality Assurance

Data security & privacy:

Paper data collection forms will be stored in a locked and secure facility only accessible by research staff at MGH in the Division of General Pediatrics at [name]. All data collected and recorded on paper forms will be entered into a Partners supported REDCap database. Only approved study staff will have access to identifiable information and the linking code. Research staff will track all communication made with parents this database including parent was contacted about the study, if the child was eligible and interested in participating, and demographic information (age, gender, parent contact info). This database will be housed on the Partners network and accessible to only IRB approved study staff.

The NIH Toolbox data will be stored on password protected iPads. The NIH Toolbox iPad application is encrypted and sends data exports (in .csv format) and participant reports (in .txt format) via secure email.

All collected data will be identified with a subject ID number only so that it cannot be matched with an individual child.

For the qualitative portion of the study, telephone interviews with parents will be recorded. To protect confidentiality, these recordings will be stored in a Partners SFL, a HIPAA compliant and encrypted format.

Maintaining the integrity of the technology

BOKS in Revere Detailed Protocol

Study PI: [name], MPH

- Research assistants and health educators will be ready to assist participants if they encounter any technical problems during the study. A support telephone number and email address will be made available to participants.
- Log of all technical difficulties will be maintained on the study database.

Monitoring and Quality Assurance

- The project manager, under direction of the Principal Investigator will monitor the study data regularly. The study staff will be appropriately trained, and the project manager will supervise data collection, storage and maintenance. The project manager will also regularly review of the accuracy and completeness of case report form entries, source documents, and informed consent.
- Research staff will evaluate the completeness of signed consent forms and questionnaires.
- The project manager will ensure that all paperwork is securely stored. The PI will ascertain appropriateness of security of all documents on a monthly basis.

Use of data

- Data collected will only be used for research purposes. Participants' anonymity will be protected in any publication of findings.
- All collaborators will be from within the Partners system.
- The only exception for data to be sent outside of Partners will be the use of an outside transcription service for the Qualitative component (Phase I) of this study. Files shared with the transcription service will be identified only by participant ID. The recordings and transcripts will be sent using a secure and encrypted online portal.

VIII. Risks and Benefits

Risk and Discomforts

As children will be physically active during these sessions, there is a risk of injury from physical activity. We do not expect these risks to be any greater than physical education lessons, which is standard practice within elementary and middle schools. It is also standard practice of schools and the BOKS program that parents sign a release form prior to allowing their child to participate in physical activity programs. Additionally, this program is currently existing in >2000 schools throughout the US and internationally, and the contents of this physical activity intervention is not unique to this research study.

It is possible that assessing weight and height may be sensitive for some children, and that answering the parental survey may be sensitive for some parents.

A breach in participant privacy and confidentiality is also a possible risk. To minimize this risk, we will use the minimum amount of PHI necessary for the proposed research. Participants are

BOKS in Revere Detailed Protocol

Study PI: [name], MPH

given an artificial study ID number that is linked through separate coding. Only study staff can link participant study ID numbers to PHI. All paper data is secured in locked file cabinets. All electronic data is secured in password protected files on computers with virus software enabled, with minimum necessary access.

Any time participant data will be transferred between MGH and a collaborator or vendor, it will be sent through a Partners approved method (i.e. Dropbox Enterprise, Syncplicity, etc).

Benefits

Potential Benefits to Participants:

Based on prior research with school-based physical activity programming as well as the BOKS program, participants in the BOKS program may benefit from improved health outcomes from increased physical activity, as well as improvements in social-emotional wellness. Students will be able to participate in the BOKS program if they do not participate in the study, so this benefit is not unique to study participation.

Potential Benefits to Society:

This study may also provide more insight on innovative methods for the implementation of physical activity interventions for children.

Appendices:

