This study is designed to assess the efficacy of a pre-existing school-based physical activity program, BOKS (“Build Our Kids Success”). BOKS is a before-school physical activity program that is currently present in over 2500 schools nationwide and internationally. Through this program, children in grades K-8 participate in before school physical activity sessions. Trained volunteers lead each session using a core curriculum developed by the BOKS leadership team that includes a warm-up game followed by activities such as relay races or obstacle courses, with a focus on a new “skill of the week” each week. In prior research, BOKS has been shown to improve child BMI as well as measures of social-emotional wellness over the 12-week program.¹²

Prior studies of physical activity interventions raise questions on whether the programs are sustainable and feasible following the end of the study period. The use of a pre-existing physical activity program aims to overcome these concerns. Additionally, by examining our primary and secondary outcomes in the BOKS program, we are evaluating the effect of the program as implemented in a real-world setting. Given the large reach of this program, the findings from this study are potentially generalizable to a larger population of students who are participants nation-wide.

III. Study Populations and Recruitment

Setting and Study Population

Students will be recruited within each of the three schools for participation in the BOKS before-school physical intervention. The participating schools include 1 middle school (541 enrolled students) and 2 elementary schools (494 and 370 enrolled students each). A flyer will be sent home with all children for program participation and parental consent/child assent for research trial participation. Target recruitment is 120-150 students total in the Spring 2018 session (40-50 per school) and 120-150 students in the Fall 2018 session (40-50 per school), for total N=240-300. Students are eligible for participation if they are in grades K – 8 with enrollment in BOKS program. The inclusion of a wait-list control group is to ensure equipoise, and that all interested students have the opportunity to participate in the physical activity program.

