As described above, this school has a pre-existing BOKS program that is independent of the research intervention and occurs as part of school-wide before school enrichment programs. Per school preference, enrollment target is approximately 40-50 students. Within this school, enrollment in the BOKS program occurs through standard school procedures for before school enrichment enrollment. Once the school has confirmed their enrollment for the Winter/Spring 2018 session, enrolled students will receive documents specific to Paul Revere, including:

- 1) BOKS study Introduction letter and Fact Sheet (Appendix 12a)
- 2) Research Consent Form (Appendix 12b)

As there will be no control group and no lottery for enrollment within this school, these documents are modified from those distributed to the other two schools and will only cover the research evaluation (not randomization and enrollment process).

Fall 2018 Session

Modifications will be made to Fall 2018 enrollment procedures based on discussions with schools as well as experience with Spring 2018 session. As program enrollment did not reach capacity in Spring 2018, no

BOKS in Revere Detailed Protocol

Study PI: [name], MPH

lottery was held and all interested students were able to participate in the program. As a result, there was no wait list control group.

In discussion with participating schools, first-come, first-serve registration will be used for Fall 2018 for consistency and no lottery will be held. If the BOKS program does not reach capacity, program registration will be accepted until program is full (40-50 students). To ensure equal access, preference will be given to students who have not previously participated in the BOKS program. In discussion with school principals, a poster (Appendix 14) will be added to increase recruitment.

In order to ease the burden of paperwork distributed via the schools, paperwork will be distributed in the following order:

1. Follow-up Letter to Previous Participants (Distributed in schools **only to consented study participants**, in envelope with student's name on it) – Appendix 15
2. Introductory letter and Fact Sheet, with Interest Form for students to return if interested (Distributed to **ALL** students) – Appendix 16
3. BOKS registration (Distributed **only to students who return Interest Form**, to be returned prior to program start) – Appendix 6b

Consent

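### The Phase II primary analysis compares intervention with control, but no comparator is defined: the Spring wait-list group did not arise and no control is named for Fall

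*Combined protocol and SAP*

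**What the plan says.** Section I, Phase II: "The primary specific aims are to examine the extent to which the physical activity intervention, compared to the control condition, results in" change in BMI and BMI z-score over 12 weeks, and change in cognitive function and quality of life.

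Section VI takes baseline-to-follow-up change in each outcome, "with comparison performed between intervention and control group at each time", by t-test and then linear regression. The listed potential confounders are age, sex, school and SES.

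Section III, Setting and Study Population, gives the control's purpose: "The inclusion of a wait-list control group is to ensure equipoise". Under Randomization, Spring 2018, a lottery was to form that group, but not at the school with a pre-existing program. Of that school, Recruitment says: "As there will be no control group and no lottery for enrollment within this school". If Spring registration did not exceed 50, "there will be no waitlist control group or need for randomization".

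Recruitment, Fall 2018 Session, then reports that Spring enrollment stayed below capacity and no lottery was held: "As a result, there was no wait list control group". Fall places are first-come, first-served. The Fall consent text adds that no further session exists to which children could be randomized.

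Remuneration (Section III), Section IV and Section V still describe an intervention group and a control group.

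**The concern.** The aim and the analysis were written for a randomized wait-list design. The recruitment text of the same version reports that the design did not materialize, yet the aim, the measurement schedule and the analysis were not revised to match. An analyst following Section VI would have to choose a comparator that the plan does not name, possibly after seeing data. A reader could then take that choice for the planned efficacy contrast. This affects every Phase II primary outcome: BMI, BMI z-score, the Flanker test and PedsQL.

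**Working it through.** **1. The plan's own total.** Section III, Setting, targets 40–50 children at each of three schools in each of two sessions: 3 × 40 × 2 = 240 and 3 × 50 × 2 = 300. This reproduces the stated 240–300. The Randomization section instead gives 80–100 per school for Spring, of whom 40–50 are wait-list controls. At the two lottery schools that makes 2 × 40 = 80 to 2 × 50 = 100 planned controls. The two recruitment targets should be reconciled when the comparator is rewritten.

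**2. Where a control was defined and where it arose.** There are 3 × 2 = 6 school-sessions.

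| School-sessions | Wait-list control defined | Status in the current text |
|---|---|---|
| Two lottery schools, Spring (2) | Yes | Reported as not having arisen |
| School with pre-existing program, Spring (1) | No | None by design |
| All three schools, Fall (3) | No | No randomization, no later session |

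A wait-list control was defined in 2 of 6 school-sessions and arose in 0 of 6. This counts wait-list arms only. Section IV expects measures in two groups in both sessions, but does not say who the second group would be.

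**3. Consequence for Spring.** The standard error of a two-group difference in mean change is SD × √(1/n₁ + 1/n₀). With n₀ = 0 it is undefined, so neither the t-test nor the group coefficient in the regression can be estimated from Spring data.

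**4. Who could be off-program in Fall.** Section III, Setting, makes BOKS enrollment an eligibility condition, so children never enrolled are outside the study. Consent, Fall 2018, keeps baseline and follow-up measurement for Spring-consented children whether or not they rejoin. Those who do not rejoin are the only off-program children with planned Fall measures. Three facts bear on using them:

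- No section names them as controls, and their number is not given.
- They have already been enrolled in BOKS, and their Fall status is not randomized.
- Prior BOKS participation is not among the listed confounders. Adding it would not help a comparison with first-time participants: every off-program child has prior enrollment and no first-timer has, so the two factors cannot be separated in that contrast.

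**5. Whether a fallback is written.** The no-control outcome was foreseen, but only as an enrollment rule. Section VI mentions within-child change only as the quantity to be compared between groups; covariate adjustment and effect modification follow that comparison. No single-group analysis is stated.

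**6. Limits on a replacement.** BMI, Flanker and PedsQL are already scheduled at baseline and 12 weeks. Secondary outcomes are less certain. Section IV gives no pre-program period for grades, attendance or disciplinary reports. It also sends no Fall survey to a parent who completed either survey in Spring, so some children may lack a pair. At the school that ran BOKS in Fall 2017, "In the school that independently held BOKS in Fall 2017, preference will be given to students who have not yet participated". That is a preference, not an exclusion, so a child's first measured session may not be the first ever.

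**The case against.** The strongest reply is that the explicit denials cover only Spring and, separately, the school with a pre-existing program. No sentence says that Fall has no control group. Section IV keeps two groups in both sessions, and the consent text keeps former participants under measurement, so an off-program group may well exist in Fall. The Spring lottery text is also labelled as Spring procedure, and the later report overtakes it without contradicting it.

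Much of this stands. A reader might infer that the protocol declares both sessions uncontrolled; it does not. The Fall absence is inferred from first-come enrollment, the lack of a later session and enrollee-only eligibility. The supportable statement is that the Fall comparator is undefined. This does not rescue Section VI, because a group that may exist but is unnamed, previously enrolled and non-randomized is not the control condition of the primary aim.

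Two further inferences go too far. One is that returning children will be displaced by the preference for new students. That is only possible: Spring did not fill, and for Fall "program registration will be accepted until program is full (40-50 students". The other is a numerical bias for using former participants as controls. It would need the true effect, the carry-over at both time points, the mix of first-time and returning children, and the selection pattern. The documents give none of these.

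**Conclusion.** The point holds and must be fixed. The Phase II primary aim and the Section VI primary analysis require an intervention-versus-control comparison for which the current text defines no comparator. The one defined control was not formed, none was planned at the third school, and none is named for Fall. Because the stated analysis is wrong as written, this is more than missing detail.

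No numerical magnitude is claimed. A Fall comparison with former participants would be open to selection and carry-over bias whose size and direction are unknown. The conclusion rests on taking the report about Spring at face value and on the inference about Fall described above. It would change if the sponsor named a concurrent Fall comparator and wrote its analysis.

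**What to change.** 1. In Sections I and VI, restate the Phase II primary aim and analysis as mean within-child 12-week change, with 95% CI, during the child's first measured BOKS session. Cover BMI, BMI z-score, Flanker and PedsQL, the last two in children aged 8 or over as in Section V. State that the result is uncontrolled and does not support an efficacy claim.
2. Do not present former participants as the control for the efficacy aim. If a Fall comparison with Spring-consented children who do not re-enrol is kept, label it observational and secondary. Adjust for baseline value and the listed confounders, and account for prior BOKS participation, for instance by comparing with Spring-consented children who do re-enrol. Report it as an association, not an effect.
3. Use paired change for secondary outcomes only where a pre-program and a follow-up value both exist.
4. Align the control-group wording in Section III (Setting, Remuneration), Section IV and Section V.

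For the primary outcomes this is a change of wording that uses measures already planned. The real cost is the weaker claim: change during the program instead of efficacy against a control. Keeping the efficacy aim would need a named concurrent comparator. If that meant children not enrolled in BOKS, the eligibility rule would have to change, with consent and measurement to match.
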